6.13. Bioanalytical and Pharmacokinetic/Pharmacodynamic Methods

Details of PK/pharmacodynamic (PD) analyses can be found in a separate PK/PD analysis plan.

6.14. Safety Analyses

The planned analyses of safety data will be performed with an intent to maintain consistency with compound level standard safety analyses. These standards are based on internal standards which were informed by Clinical Data Interchange Standards Consortium (CDISC) standards, regulatory guidance (eg, FDA Clinical Review Template), and cross-industry standardization efforts (eg, Pharmaceutical Users Software Exchange [PhUSE] white papers from the Standard Analyses and Code Sharing Working Group provided in the PhUSE Computational Science Deliverables Catalog).

Safety evaluations will be based upon the following safety analysis populations with their associated study periods, unless specified otherwise:

- Modified Safety Population (Induction Period),
- Safety Population (Induction Period) as a sensitivity analysis,
- Modified Maintenance Primary Population (Maintenance Blinded Period),
- Maintenance Primary Population (Maintenance Blinded Period) as a sensitivity analysis,
- All Lebrikizumab Modified Safety Population (Combined Induction and Maintenance Periods, and Combined Induction and Maintenance Periods plus Follow Up Period [selective analysis])
- All Lebrikizumab Safety Population (Combined Induction and Maintenance Periods, and Combined Induction and Maintenance Periods plus Follow Up Period [selective analysis]) as a sensitivity analysis.

These analysis populations are fully defined in [Table KGAC.6.1](#) while [Table KGAC.6.2](#) describes the treatment groups, associated study periods, and the comparisons for each analysis population.

Selected safety summaries as sensitivity analysis will be conducted on Safety Population, Maintenance Primary Population, and All Lebrikizumab Safety Population, including overview of AEs, Summary of TEAE PTs by maximum severity and a listing of TEAEs that occurred in the safety population but not in modified safety population.

For document writing purposes for safety, tests with two-sided p-values less than 0.05 will be referred to as having strong statistical evidence for a treatment difference, unless otherwise noted. However, p-values should not be over-interpreted for these safety analyses. Except for pre-specified hypotheses, they correspond to data-driven hypotheses and hence are only useful as a flagging mechanism.

Not all displays described in this section will necessarily be included in the CSRs. Any display described and not provided in the CSR would be available upon request. Not all displays will necessarily be created as a “static” display. Some may be incorporated into interactive display tools instead of or in addition to a static display. Any display created interactively will be included in the CSR if deemed relevant to the discussion.

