1.3.1.3. Summary of Dose Ranging Study DRM06-AD01

Study Design

DRM06-AD01 was a Phase 2b, randomized, double-blind, placebo-controlled, dose-ranging study to evaluate the safety and efficacy of lebrikizumab in adult patients with moderate to severe AD. A total of 280 patients were randomized to 1 of 4 treatment groups (in a 3:3:3:2 ratio): 73 to lebrikizumab 125 mg Q4W (with a loading dose of 250 mg); 80 to lebrikizumab 250 mg Q4W (with a loading dose of 500 mg); 75 to lebrikizumab 250 mg Q2W (with a loading dose of 500 mg given at baseline and Week 2); 52 to placebo Q2W.

Efficacy Results

- Statistically significantly greater proportions of patients in each of the lebrikizumab 250 mg Q4W and 250 mg Q2W groups achieved EASI-50, EASI-75, or EASI-90 at Week 16 than the placebo group.
- A statistically significantly greater proportion of patients in each of the lebrikizumab 250 mg Q4W and 250 mg Q2W groups had both an IGA score of 0 or 1 and a ≥ 2 -point improvement in IGA score at Week 16 than the placebo group.
- The lebrikizumab 250 mg Q2W group had a statistically significantly greater proportion of patients who achieved a ≥ 4 -point improvement in pruritus NRS compared with the placebo group.
- Positive changes in pruritus correlated with positive changes in sleep; the lebrikizumab 250 mg Q4W and 250 mg Q2W groups had statistically significant percent reductions in sleep loss due to itching compared with placebo ($p=0.0459$ and $p=0.0062$, respectively).

Safety Results

- The incidences of conjunctivitis (2.6% all lebrikizumab groups, 0 placebo), herpes infections (2.2% all lebrikizumab groups, 0 placebo), and herpes zoster (0.9% all lebrikizumab groups, 0 placebo) were relatively low.
- Three patients (1.3%) in the lebrikizumab groups and 2 patients (3.8%) in the placebo group had an SAE. Those reported in the lebrikizumab groups were severe chest pain (1 patient in the 250 mg Q2W group), femur fracture of moderate severity (1 patient in the 125 mg Q4W group), and panic attack of moderate severity (1 patient in the 250 mg Q2W group). Those reported in the placebo group were severe chronic obstructive pulmonary disease, severe edema peripheral, and severe pulmonary embolism. All SAEs were considered by the investigator as not related to study drug.
- Most AEs were considered not related to study drug; those considered related were reported for 16.2% of patients in the lebrikizumab groups and 5.8% of patients in the placebo group

Conclusions

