For variables that are not collected at each postbaseline visit, data may exist at visits where the variable was not scheduled to be collected. In these situations, data from the early discontinuation visit that do not correspond to the planned collection schedule will be excluded from the MMRM analysis (Andersen and Millen 2013). Also for by-visit summaries/displays such as boxplots, the weeks when data was not scheduled to be collected may not be displayed. However, unscheduled assessments within any defined study period will still be used in the shift analyses, and for imputing values for the change from baseline to last observation carried forward (LOCF) endpoint analyses.

The Kaplan-Meier (KM) product limit method maybe used to estimate the survival for time to event analyses. The log-rank test stratified by the stratification factors mentioned in Section 6.3 will be reported. A Kaplan-Meier plot of the time to event by treatment group may be provided.

Unless specified otherwise, Fisher's exact test will be used for adverse events (AEs) and other categorical safety measures. Odds ratios will be created with lebrikizumab treatment as the numerator, and placebo as the denominator. Continuous vital sign and laboratory values will be analyzed by an ANCOVA with treatment and baseline value in the model.

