6.14.2. Adverse Events

A TEAE is defined as an event that first occurred or worsened in severity after baseline. The MedDRA Lowest Level Term (LLT) will be used in the treatment-emergent computation. The maximum severity for each LLT during the baseline period will be used as baseline. The treatment period will be included as postbaseline for the analysis. For events with a missing severity during the baseline period, it will be treated as 'mild' in severity for determining treatment-emergence. Events with a missing severity during the postbaseline period will be treated as 'severe' and treatment-emergence will be determined by comparing to baseline severity. For events occurring on the day of first taking study medication, it will be assumed to be posttreatment.

The planned summaries for adverse events are provided in [Table KGAC.6.13](#), and are described more fully in compound level safety standards and in the adverse event-related PhUSE white paper [Analysis and Displays Associated with Adverse Events: Focus on Adverse Events in Phase 2-4 Clinical Trials and Integrated Summary Document (PhUSE 2017)].

Summary tables as described in [Table KGAC.6.13](#) will be presented for the following periods/analysis populations as indicated. Summary tables will include the number and percentage of patients reporting an event. For events that are gender-specific (as defined by MedDRA), the number of participants at risk will include only patients from the given gender.

- Induction Period (Modified Safety Population, mS)
- Induction Period (Safety Population, S) as a sensitivity analysis
- Maintenance Blinded Period (Modified Maintenance Primary Population, mM)
- Maintenance Blinded Period (Maintenance Primary Population, M) as a sensitivity analysis
- Combined Induction Period and Maintenance Period, Combined Induction and Maintenance Periods Plus Follow-Up Period [selective analysis] (All Lebrikizumab Modified Safety Population, mA)
- Combined Induction Period and Maintenance Period, Combined Induction and Maintenance Periods Plus Follow-Up Period [selective analysis] (All Lebrikizumab Safety Population, A) as a sensitivity analysis

Table KGAC.6.13. Summary Tables/Listing Related to Adverse Events

Analysis	Population (Section 6.1.1)
Overview of AEs	mS, S, mM, M, mA, A
Summary of TEAE by PTs	mS, mM
Summary of TEAE by PTs occurring in $\geq 1\%$ of patients	mS, mM
Summary of TEAE by PTs within SOC	mS, mM, mA

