Summary of TEAE PTs by maximum severity	mS, S, mM, M
Summary of SAE by PT within SOC	mS, mM, mA
Summary of AEs leading to treatment discontinuation by PT with SOC	mS, mM, mA
Summary of TEAEs possibly related to study drug by PTs within SOC	mS, mM
Listing of SAEs (including Death)	ITT
Listing of primary AEs leading to study treatment discontinuation	ITT
Listing of TEAEs (for Japan submission only)	S
Listing of TEAEs occurred in safety population but not in modified safety population	

Abbreviations: A = All Lebrikizumab Safety Population; AE = adverse event; ITT = Intent-to-Treat; M = Maintenance Primary Population; mA = Modified All Lebrikizumab Safety Population; mM = Modified maintenance Primary Population, mS = Modified Safety Population; PT = Preferred Term; S = Safety Population; SAE = serious adverse event; SOC = System Organ Class; TEAE = treatment-emergent adverse event.

Statistical comparisons will be performed using Fisher's exact test. Odds ratio will be provided.

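### Adverse event comparisons are planned with Fisher's test and an odds ratio only: no confidence interval, and no estimate that stays finite when placebo has zero events

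*SAP*

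**What the plan says.** SAP 6.14.2, below the table of AE displays, gives the comparative analysis: "Statistical comparisons will be performed using Fisher's exact test. Odds ratio will be provided". SAP 6.1.2 sets the direction for the Induction Period: "Odds ratios will be created with lebrikizumab treatment as the numerator, and placebo as the denominator". SAP 6.1.3.1 repeats the same test and ratio for the Maintenance Blinded Period. None of the three gives the safety odds ratio a confidence interval, a zero-cell rule or a companion risk difference.

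SAP 6.14 sets a writing convention: "tests with two-sided p-values less than 0.05 will be referred to as having strong statistical evidence for a treatment difference". It then qualifies it: "However, p-values should not be over-interpreted for these safety analyses". It adds that, apart from pre-specified hypotheses, such p-values "hence are only useful as a flagging mechanism".

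Two other parts of the plan matter here. AE displays carry frequencies: "Summary tables will include the number and percentage of patients reporting an event". And SAP 6.1.2 treats binary efficacy endpoints differently: they get a common risk difference with a 95% CI and an odds ratio with a 95% CI.

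On expected events, Protocol 1.3.1.3 reports for Phase 2b: "The incidences of conjunctivitis (2.6% all lebrikizumab groups, 0 placebo), herpes infections (2.2% all lebrikizumab groups, 0 placebo". The same summary puts zoster at 0.9% on lebrikizumab, with no placebo case. Protocol 1.3.1.1 reports allergic conjunctivitis in 8 of 156 lebrikizumab patients (5.1%) and herpes viral infections and zoster in 6 of 156 (3.8%) in the Phase 2a study, with none on placebo for either. Protocol 8.5.4.2 designates conjunctivitis and herpes infection or zoster as AESIs.

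**The concern.** The study objective names safety as well as efficacy, and both documents give sufficient safety information as one reason for raising the sample size to about 400. The events designated as AESIs are also the ones for which the earlier studies recorded nothing on placebo. That is where the chosen effect measure breaks down: with an empty placebo cell the odds ratio has no finite value, and the plan does not say what will be printed.

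What then remains beside the raw frequencies is a p-value that, at these event rates and this trial size, will usually exceed 0.05. The caution in 6.14 is directed at reading too much into small p-values. It does not say how a large one should be read, and it supplies no measure of precision. A safety narrative could report a numerical imbalance on an AESI without strong statistical evidence and give no upper limit on the excess risk.

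**Working it through.** **The plan's own power figure.** The documents state power for efficacy only. For IGA 0/1 at 34.7% versus 7.7% with 96 versus 48 patients, the continuity-corrected chi-square formula gives 95.1%, and for EASI-75 at 48.0% versus 11.5% it gives 99.6%. Both agree with the stated figure of more than 95%. There is no stated power or detectable rate for safety to reproduce.

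**Inputs.** About 400 patients at 2:1 (SAP 5.2), taken as 267 versus 133. Two-sided 0.05 (SAP 6.14). Lebrikizumab rates of 2.6%, 2.2% and 0.9% (Protocol 1.3.1.3), and 5.1% and 3.8% (Protocol 1.3.1.1). The true placebo rate is an assumption: 0, with 0.5% and 1% as a range.

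**Step 1: events needed for the label.** With k events in all and none on placebo, the probability of the observed table is C(267,k)/C(400,k). The two-sided p adds every table at most that likely.
- k = 9: 0.02513 + (0.00004 + 0.00079 + 0.00670) = 0.033.
- k = 8: 0.03804 + (0.00013 + 0.00219 + 0.01607) = 0.056.

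So 9 versus 0 is the minimum, and 9/267 = 3.4%. At 7 versus 0, p = 0.10; at 6 versus 0, p = 0.18; at 2 versus 0, p = 1.0.

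**Step 2: chance of the label.** With a true placebo rate of 0 this is P(X ≥ 9), where X is binomial(267, rate). With a non-zero placebo rate, both binomial counts are enumerated.

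| Lebrikizumab rate | Expected events (267 × rate) | Placebo 0 | Placebo 0.5% | Placebo 1% |
|---|---|---|---|---|
| 0.9% (zoster, Phase 2b) | 2.4 | 0.1% | <0.1% | <0.1% |
| 2.2% (herpes, Phase 2b) | 5.9 | 14% | 7% | 4% |
| 2.6% (conjunctivitis, Phase 2b) | 6.9 | 26% | 14% | 8% |
| 3.8% (herpes and zoster, Phase 2a) | 10.1 | 69% | 43% | 27% |
| 5.1% (allergic conjunctivitis, Phase 2a) | 13.6 | 93% | 72% | 53% |

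Against a zero placebo rate, about 4.25% on lebrikizumab is needed for 80%. With arms of 260/130 to 283/141, the Phase 2b figures against zero range over 24–32%, 12–17% and about 0.1%.

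**Step 3: how often the placebo cell is empty.** 0.995^133 = 51% at a 0.5% placebo rate, and 0.99^133 = 26% at 1%.

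**Step 4: what each measure shows at 7/267 versus 0/133.**
- Sample odds ratio: (7 × 133)/(260 × 0), infinite. Adding 0.5 to each cell gives (7.5 × 133.5)/(260.5 × 0.5) = 7.7. The exact conditional 95% interval starts at 0.72 and has no upper limit. The plan does not choose among these.
- Risk difference: 7/267 − 0 = 2.6%. The Wilson limits are 1.28% to 5.31% on lebrikizumab and 0 to 2.81% on placebo. Newcombe lower limit: 2.62 − √[(2.62 − 1.28)² + 2.81²] = −0.5%. Upper limit: 2.62 + (5.31 − 2.62) = 5.3%.

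The risk difference and its limits are finite, and the upper limit of 5.3% is the information that the planned output lacks.

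**The case against.** A reader might infer that p < 0.05 is the SAP's only safety signal rule, that imbalances of the Phase 2b size would go unnoticed, or that no usable effect size would exist. The documents support none of these.

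- The sentence in 6.14 is a caveated wording convention, and the odds ratio carries no threshold. Other screens do not depend on p: common TEAEs at 1% or more (6.14.2.1), liver-test multiples (6.14.6.1), laboratory and vital-sign shifts, and DSMB review (6.17).
- Conjunctivitis and herpes have their own summaries and patient listings whatever the p-value (6.14.6.3 and 6.14.6.4). Only the p < 0.05 label would be missed.
- Counts and percentages by arm allow a reader to subtract. What is missing is the stated uncertainty.

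Four further points carry weight. The Phase 2b rates pool three dose regimens, so the rate at 250 mg Q2W is not given. The Phase 2b excess is not itself established: 6/228 versus 0/52 gives p = 0.60. Low power comes from the trial's size, and the proposed interval for 7 versus 0 also includes zero, so it flags nothing more. Finally, SAP 6.14.2 and 6.14.6 refer to compound level safety standards that may already require intervals; they were not available to check.

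These points limit the finding to precision and zero-cell handling. They do not supply the missing interval, and the DSMB's advice during the trial does not provide the report's effect estimates.

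**Conclusion.** The point holds as a reporting gap that is cheap to close. For AE comparisons the SAP as written gives a test and an estimator without an interval, and the estimator has no finite value when placebo has no events. At the pooled Phase 2b rates the p < 0.05 label would appear in roughly a quarter of trials or fewer, so its absence would say little; at 5.1% versus 0 it would appear in about 93%. The excess would be visible in the tables, but no bound on it is planned.

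This rests on arms of about 267 and 133 in the safety set (the number removed with Site 5042 is not given), independent binomial counts, Phase 2 rates carrying over, and a placebo rate at or near zero. It is conditional on the compound level safety standards not already specifying an interval. Nothing in the documents says that p ≥ 0.05 will be read as no signal; the point is that the SAP does not rule that reading out.

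**What to change.** Unless the compound level safety standards already do so:

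1. In SAP 6.1.2, 6.1.3.1 and 6.14.2, report beside the odds ratio the risk difference versus placebo with a two-sided 95% CI by a named method valid at zero cells (Newcombe or Miettinen-Nurminen), at least for AESIs, SAEs and common TEAEs.
2. In SAP 6.14, state that p ≥ 0.05 is not read as absence of a difference.

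The cost is SAP wording and extra columns in the AE tables, with no new data or patients. The downside is visibly wide intervals. The change adds information on precision; it does not raise the power to detect a difference.

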6.14.1. Extent of Exposure

Duration of exposure to study treatment will be summarized by treatment group. Drug interruption time period due to the use of systemic rescue therapies will not be removed from study drug exposure calculations as described in compound level safety standards.

The duration of exposure will be calculated as:

Duration of exposure (days)

$$= \text{Date of last visit (scheduled or unscheduled) in the specified Treatment Period} \\ - \text{Date of first dose in Treatment Period} + 1$$

The number and percentage of patients in each of the following categories will be included in the summaries:

- $>0, \geq 7, \geq 14, \geq 30, \geq 60, \geq 90, \geq 112, \geq 120$ days for Induction Period (for Maintenance Period, use $\geq 30, \geq 60, \geq 90, \geq 120, \geq 150, \geq 180, \geq 210, \geq 240$, and ≥ 252 days). Note that patients may be included in more than 1 category.
- >0 to $<7, \geq 7$ to $<14, \geq 14$ to $<30, \geq 30$ to $<60, \geq 60$ to $<90, \geq 90$ to $<120, \geq 120$ days (for Maintenance Period, use >0 to $<30, \geq 30$ to $<60, \geq 60$ to $<90, \geq 90$ to $<120, \geq 120$ to $<150, \geq 150$ to $<180, \geq 180$ to $<210, \geq 210$ to $<240, \geq 240$ to $<252, \geq 252$).

Additional exposure ranges may be considered if necessary. No p-values will be reported.

The summaries will also include the following information:

- Total exposure in patient years, calculated as:

Total exposure in patient years

$$= \frac{\text{Sum of duration of exposures for all patients in treatment group}}{365.25}$$

- Mean and median total dose. Total dose (in mg) is calculated by the number of active injections taken during the treatment period multiplied by dose. For patients in Safety Population randomized to lebrikizumab 250 mg Q2W or patients in Maintenance Primary Population re-randomized to lebrikizumab 250 mg Q2W or Q4W, the total dose (in mg) taken during Induction Period or Maintenance Period will be calculated as follows: *Total lebrikizumab dose = Total number of active injections (including loading doses, if any) received in Induction Period or Maintenance Period × 250.*
- Total number of injections received will be derived based on the *Study Drug Administration* eCRF page and the response to the question “Did you or a caregiver successfully inject the study drug?” on the *Dosing Diary* eCRF page.

The exposure for the All Lebrikizumab Modified Safety Population during the Combined Induction and Maintenance Periods will be calculated as (Date of last study visit during Treatment Period – Date of first lebrikizumab injection +1 day) calculated for each treatment period where the patient receives lebrikizumab and then summed together (this excludes the duration of time that patients are receiving placebo during the Maintenance Period). If a patient was randomized to lebrikizumab during Induction Period, then to placebo during Maintenance

Period and later on entered escape arm following loss of response (<EASI-50), the patient's exposure on lebrikizumab during Maintenance Period will be calculated (Date of last study visit during Maintenance Period– Date of first injection to resume lebrikizumab + 1 day) and will be added to the exposure in the Induction Period.

The exposure for the All Lebrikizumab Modified Safety Population during the Combined Induction and Maintenance Periods plus Follow up Period will be calculated as the time between the first dose of LY and the study treatment disposition visit plus any follow-up period.

6.14.2. Adverse Events

A TEAE is defined as an event that first occurred or worsened in severity after baseline. The MedDRA Lowest Level Term (LLT) will be used in the treatment-emergent computation. The maximum severity for each LLT during the baseline period will be used as baseline. The treatment period will be included as postbaseline for the analysis. For events with a missing severity during the baseline period, it will be treated as 'mild' in severity for determining treatment-emergence. Events with a missing severity during the postbaseline period will be treated as 'severe' and treatment-emergence will be determined by comparing to baseline severity. For events occurring on the day of first taking study medication, it will be assumed to be posttreatment.

The planned summaries for adverse events are provided in [Table KGAC.6.13](#), and are described more fully in compound level safety standards and in the adverse event-related PhUSE white paper [Analysis and Displays Associated with Adverse Events: Focus on Adverse Events in Phase 2-4 Clinical Trials and Integrated Summary Document (PhUSE 2017)].

Summary tables as described in [Table KGAC.6.13](#) will be presented for the following periods/analysis populations as indicated. Summary tables will include the number and percentage of patients reporting an event. For events that are gender-specific (as defined by MedDRA), the number of participants at risk will include only patients from the given gender.

- Induction Period (Modified Safety Population, mS)
- Induction Period (Safety Population, S) as a sensitivity analysis
- Maintenance Blinded Period (Modified Maintenance Primary Population, mM)
- Maintenance Blinded Period (Maintenance Primary Population, M) as a sensitivity analysis
- Combined Induction Period and Maintenance Period, Combined Induction and Maintenance Periods Plus Follow-Up Period [selective analysis] (All Lebrikizumab Modified Safety Population, mA)
- Combined Induction Period and Maintenance Period, Combined Induction and Maintenance Periods Plus Follow-Up Period [selective analysis] (All Lebrikizumab Safety Population, A) as a sensitivity analysis

Table KGAC.6.13. Summary Tables/Listing Related to Adverse Events

Analysis	Population (Section 6.1.1)
Overview of AEs	mS, S, mM, M, mA, A
Summary of TEAE by PTs	mS, mM
Summary of TEAE by PTs occurring in $\geq 1\%$ of patients	mS, mM
Summary of TEAE by PTs within SOC	mS, mM, mA
Summary of TEAE PTs by maximum severity	mS, S, mM, M
Summary of SAE by PT within SOC	mS, mM, mA
Summary of AEs leading to treatment discontinuation by PT with SOC	mS, mM, mA
Summary of TEAEs possibly related to study drug by PTs within SOC	mS, mM
Listing of SAEs (including Death)	ITT
Listing of primary AEs leading to study treatment discontinuation	ITT
Listing of TEAEs (for Japan submission only)	S
Listing of TEAEs occurred in safety population but not in modified safety population	

Abbreviations: A = All Lebrikizumab Safety Population; AE = adverse event; ITT = Intent-to-Treat; M = Maintenance Primary Population; mA = Modified All Lebrikizumab Safety Population; mM = Modified maintenance Primary Population, mS = Modified Safety Population; PT = Preferred Term; S = Safety Population; SAE = serious adverse event; SOC = System Organ Class; TEAE = treatment-emergent adverse event.

Statistical comparisons will be performed using Fisher's exact test. Odds ratio will be provided.

